## MSSM Protocol Template HRP-503a

### Instructions:

1. Prepare a document with the following sections. Note that, depending on the nature of your research, certain sections below may not be applicable. Indicate N/A as appropriate, explaining where possible.
2. For any items described in the sponsor's protocol, grant application or other source documents submitted with the application, you may reference the title and page numbers of these documents rather than cutting and pasting into this document. **Do NOT refer to any derived documents, such as the Sample Consent document, or other internal documents required with the submission.**
3. If you reference page numbers, attach those pages to this protocol.
4. When you write a protocol, keep an electronic copy. You will need to modify this copy when making changes.

### Brief Summary of Research (250-400 words):

The QL 2 block is a novel fascial plane block recently described by Blanco and colleagues in which local anesthetic is deposited adjacent to the antero-lateral aspect of the quadratus lumborum muscle. This results in posterior spread of local anesthetic through the middle layer of the thoraco-lumbar fascia, which theoretically communicates with the paravertebral space resulting in potentially longer-lasting and denser analgesia than wound infiltration. The QL 2 block derives from the TAP block, which is also a fascial plane block that is commonly used to treat pain following surgery involving the anterior abdominal wall. However, the QL block's more posterior location has recently been shown to provide a longer lasting and more profound analgesic effect than the TAP block, possibly by communicating with

|   |  |
|---|--|
| Protocol Title:                           | QUADRATUS LUMBORUM II BLOCK VS CONVENTIONAL THERAPY ALONE FOR LAPAROSCOPIC SLEEVE GASTRECTOMY  |
| Principal Investigator Name/Contact Info: | [name] MD
[contact]   |
| Primary Contact Name/Contact Info         | [name] MD
[contact]
[contact]
[name] MD
[contact]
[contact]
[name] MD
[name] MD
[name] DO
[name] MD |
| Date Revised:                             | 1/10/2018  |
| Study Number:                             | IF 2203362   |

the paravertebral space. Although the TAP has been shown to be effective in a variety of surgical procedures involving an anterior abdominal wall incision including laparoscopic bariatric surgery the QL 2 block has until now, not been studied in the context of bariatric surgery.

## 1) Objectives:

### ***Research Question:***

Is the quadratus lumborum (QL) II block superior to conventional therapy consisting of wound infiltration with bupivacaine 0.25%, for postoperative analgesia following laparoscopic gastric sleeve gastrectomy?

### ***Primary outcome:***

The amount of opioid consumption (in mg IV morphine equivalents) during the first 48 hours after the procedure.

### ***Secondary outcomes:***

|   |   |  |
|---|---|--|
|  | Protocol Title:                           | QUADRATUS LUMBORUM II BLOCK VS CONVENTIONAL THERAPY ALONE FOR LAPAROSCOPIC SLEEVE GASTRECTOMY  |
|   | Principal Investigator Name/Contact Info: | [name] MD
[contact]   |
|   | Primary Contact Name/Contact Info         | [name] MD
[contact]
[contact]
[name] MD
[contact]
[contact]
[name] MD
[name] MD
[name] DO
[name] MD |
|   | Date Revised:                             | 1/10/2018  |
|   | Study Number:                             | IF 2203362   |
|   |   |  |

VAS pain scores on arrival to PACU and at 1, 2, 24, and 48 hours.

Extent of blockade as determined by pin prick, itching, nausea, vomiting in PACU.

Respiratory rate, heart rate, and blood pressure on arrival, 1 hour after arrival to PACU and departure from PACU.

Time to first dose of opioid administration in the PACU, as well as location and type (visceral or somatic) of pain.

## 2)Background

The QL 2 block is a novel fascial plane block recently described by Blanco and colleagues in which local anesthetic is deposited adjacent to the antero-lateral aspect of the quadratus lumborum muscle. This results in posterior spread of local anesthetic through the middle layer of the thoraco-lumbar fascia, which theoretically communicates with the paravertebral space resulting in potentially longer-lasting and denser analgesia than wound infiltration. Like the more commonly used transversus abdominis plane (TAP) block, the QL 2 block targets the anterior rami of T7-T12, ilioinguinal, iliohypogastric, and the lateral cutaneous branches of L1-L3. The QL 2 block derives from the TAP block, which is also a fascial plane block that is commonly used to treat pain following surgery involving the anterior abdominal wall. However, the QL block's more posterior location has recently been shown to provide a longer lasting and more profound analgesic effect than the TAP block, possibly by communicating with the paravertebral space.

|   |  |
|---|--|
| Protocol Title:                           | QUADRATUS LUMBORUM II BLOCK VS CONVENTIONAL THERAPY ALONE FOR LAPAROSCOPIC SLEEVE GASTRECTOMY  |
| Principal Investigator Name/Contact Info: | [name] MD
[contact]   |
| Primary Contact Name/Contact Info         | [name] MD
[contact]
[contact]
[name] MD
[contact]
[contact]
[name] MD
[name] MD
[name] DO
[name] MD |
| Date Revised:                             | 1/10/2018  |
| Study Number:                             | IF 2203362   |

Although the TAP has been shown to be effective in a variety of surgical procedures involving an anterior abdominal wall incision including laparoscopic bariatric surgery the QL 2 block has until now, not been studied in the context of bariatric surgery. Conventional therapy has consisted of surgical infiltration of the incision ports with bupivacaine 0.25%. We propose a study to compare the analgesic effects of the QL 2 block with conventional therapy, consisting of surgical wound infiltration, for postoperative analgesia following laparoscopic gastric sleeve gastrectomy.

### 3)Setting of the Human Research

This is a prospective, double blind, randomized control trial in patients undergoing sleeve gastrectomy surgeries. The research study will take place at Mount Sinai St. Luke's hospital. The PI is [name].

### 4)Resources Available to Conduct the Human Research

For n=110, the feasibility of recruitment is manageable as we perform 5-10 sleeve gastrectomies per week on average. Recruitment will be done through a coordination of the operating schedule and the surgeon's office. Patients presenting for preoperative visits at the preoperative testing clinic will be approached. Patients routinely are seen by anesthesiologists at the preoperative testing clinic as part of their anesthetic evaluation. Patients will be approached by research personnel only if the patients are agreeable to the study and details of the study will be explained. The consent will be obtained in the pre operative testing clinic or in the pre operative holding area after all questions are thoroughly answered. The staff members on this protocol are all employees of Mount Sinai and will either be a resident or attending

|   |  |
|---|--|
| Protocol Title:                           | QUADRATUS LUMBORUM II BLOCK VS CONVENTIONAL THERAPY ALONE FOR LAPAROSCOPIC SLEEVE GASTRECTOMY  |
| Principal Investigator Name/Contact Info: | [name] MD
[contact]   |
| Primary Contact Name/Contact Info         | [name] MD
[contact]
[contact]
[name] MD
[contact]
[contact]
[name] MD
[name] MD
[name] DO
[name] MD |
| Date Revised:                             | 1/10/2018  |
| Study Number:                             | IF 2203362   |

physicians that are included on the IRB protocol. There are seven primary members of the research personnel:

a) [name]. – Roles for [name] in this study include serving as primary investigator responsible for study design and planning, data collection, subject recruitment, manuscript writing and preparation, data analysis, safety monitoring, and responding to adverse events and/or complications. He is certified in PPHS/IRB protocols, all Citi/IRB required training in human subject protection, and has prior clinical research experience. He is also a board certified anesthesiologist and assistant professor of anesthesiology with the Icahn School of Medicine and the Mount Sinai Health System.

| Protocol Title:                           | QUADRATUS LUMBORUM II BLOCK VS CONVENTIONAL THERAPY ALONE FOR LAPAROSCOPIC SLEEVE GASTRECTOMY  |
| Principal Investigator Name/Contact Info: | [name] MD
[contact]   |
| Primary Contact Name/Contact Info         | [name] MD
[contact]
[contact]
[name] MD
[contact]
[contact]
[name] MD
[name] MD
[name] DO
[name] MD |
| Date Revised:                             | 1/10/2018  |
| Study Number:                             | IF 2203362   |

There are institutional processes to ensure that all persons assisting with the protocol will be well informed. The research personnel will conduct regular meetings and department email updates to review the results and safety data of the study. The research personnel will initiate the formation of a safety monitoring board for adverse effects, complications, or complaints from patient subjects.

## 5) Study Design

### b) Recruitment Methods

This project will be a prospective double blinded randomized control trial.

Recruitment will be done through a coordination of the operating schedule and the offices of bariatric surgeons who have agreed to allow us to approach their patients regarding recruitment for the study. Patients presenting for preoperative visits at the preoperative testing clinic at St. Luke's Hospital will be approached. Patients routinely are seen by anesthesiologists at the pre operative testing clinic as part of pre operative anesthetic evaluation. Patients will be approached by research personnel only if the patients are agreeable to the study and details of the study will be explained. The consent will be obtained in

|   |   |  |
|---|---|--|
|  | Protocol Title:                           | QUADRATUS LUMBORUM II BLOCK VS CONVENTIONAL THERAPY ALONE FOR LAPAROSCOPIC SLEEVE GASTRECTOMY  |
|   | Principal Investigator Name/Contact Info: | [name] MD
[contact]   |
|   | Primary Contact Name/Contact Info         | [name] MD
[contact]
[contact]
[name] MD
[contact]
[contact]
[name] MD
[name] MD
[name] DO
[name] MD |
|   | Date Revised:                             | 1/10/2018  |
|   | Study Number:                             | IF 2203362   |
|   |   |  |

the pre-operative testing clinic or in the pre operative holding area after all questions are thoroughly answered.

Patients who meet the inclusion criteria will be recruited. The team will finalize participation and ask the subject to sign the study consent forms. All patients will be provided with copies of the IRB protocol and consent if they wish to have it. Copy of the consent form will be sent in a secured email to the potential subject. The email will be secured by entering in [SECURE] in the e-mail subject line. Once recruited blinding assessments will be done by the study team.

Patients will be assigned randomly using a computer- generated table of numbers to either QL 2 block (QL group) or wound infiltration (conventional therapy group). The anesthesia team will perform all blocks. The resident anesthesiologist will know the group allocation but will not be involved in the study. Conventional therapy consists of the injection of 30 mL of bupivacaine 0.25% directly into the incision sites by the surgeon at the end of the procedure.

The QL 2 group will receive 15 mL bupivacaine 0.25% on both sides for a total of 30 mL once the surgery is done but prior to extubation.

Then anesthesiologist performing the QL 2 block will be different from the anesthesiologist assessing the patient after surgery.

The patient and anesthesiologist assessing the patient will be blinded.

|   |  |
|---|--|
| Protocol Title:                           | QUADRATUS LUMBORUM II BLOCK VS CONVENTIONAL THERAPY ALONE FOR LAPAROSCOPIC SLEEVE GASTRECTOMY  |
| Principal Investigator Name/Contact Info: | [name] MD
[contact]   |
| Primary Contact Name/Contact Info         | [name] MD
[contact]
[contact]
[name] MD
[contact]
[contact]
[name] MD
[name] MD
[name] DO
[name] MD |
| Date Revised:                             | 1/10/2018  |
| Study Number:                             | IF 2203362   |

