### f) Procedures Involved in the Human Research

|   |   |  |
|---|---|--|
|  | Protocol Title:                           | QUADRATUS LUMBORUM II BLOCK VS CONVENTIONAL THERAPY ALONE FOR LAPAROSCOPIC SLEEVE GASTRECTOMY  |
|   | Principal Investigator Name/Contact Info: | [name] MD
[contact]   |
|   | Primary Contact Name/Contact Info         | [name] MD
[contact]
[contact]
[name] MD
[contact]
[contact]
[name] MD
[name] MD
[name] DO
[name] MD |
|   | Date Revised:                             | 1/10/2018  |
|   | Study Number:                             | IF 2203362   |
|   |   |  |

Patients will be randomized to receive either QL 2 block or standard therapy, which consists of the injection of 30 mL of bupivacaine 0.25% directly into the incision site by the surgeon at the end of the procedure. The QL 2 group will receive 15 mL bupivacaine 0.25% on both sides for a total of 30 mL.

All patients will receive general anesthesia (GA) with an endotracheal tube. Patients will be brought to the operating room and general anesthesia will be induced with midazolam 1-2 mg, fentanyl 1-2 mcg/kg, propofol 2-3 mg/kg, and succinylcholine 0.6 mg/kg followed by intubation of the trachea.

For the QL 2 group, after the surgical procedure is finished and before extubation, the abdomen will be sterilized with chlorhexidine prep and time out performed according to universal protocol. A curved, low frequency probe (5-8 MHz) with an imaging depth set between 1-9 cm will be used. For the QL 2 block, the probe will be placed at the anterior superior iliac spine at the level of the mid-axillary line and moved cranially until the three muscles of the abdominal wall: external oblique, internal oblique, and transversus abdominis (from superficial to deep) are identified. The probe will then be moved postero-laterally until the posterior border of the external oblique is visualized. At this point, the internal oblique forms a roof over the quadratus lumborum and the middle layer of the thoracolumbar fascia can then be visualized as a hyperechoic band investing the quadratus lumborum muscle. A

|   |  |
|---|--|
| Protocol Title:                           | QUADRATUS LUMBORUM II BLOCK VS CONVENTIONAL THERAPY ALONE FOR LAPAROSCOPIC SLEEVE GASTRECTOMY  |
| Principal Investigator Name/Contact Info: | [name] MD
[contact]   |

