| Primary Contact Name/Contact Info         | [name] MD
[contact]
[contact]
[name] MD
[contact]
[contact]
[name] MD
[name] MD
[name] DO
[name] MD |
| Date Revised:                             | 1/10/2018  |
| Study Number:                             | IF 2203362   |

10 cm, 21-gauge block needle will be inserted from an anterior to posterior direction followed by injection of 15 mL of bupivacaine 0.25% on each side for a total of 30 mL.

All patients will receive IV acetaminophen 1000 mg and IV ketorolac 30 mg, as well as, fentanyl 25-50 mcg prn for intraoperative pain when the HR and/or SBP increase to above 20% of baseline. Postoperatively, all patients will receive acetaminophen 1000 mg IV q6h for a total of 4 doses, ketorolac 15 mg IV q6h for a total of 4 doses, and hydromorphone 0.3 mg IV q4h prn for severe pain (>6 on the VAS pain scale).

Patients will be evaluated by research personnel who are blinded as to which treatment the patient received. The first evaluation will be on arrival and one hour after arrival in the PACU. This will consist of sensory exam by pinprick to determine the extent of the block, VAS pain scores, opioid consumption, assessment of nausea and/or vomiting, and documentation of vital signs like respiratory rate, heart rate, and blood pressure will be recorded in PACU as well.

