### 6) Risks to Subjects

Systemic absorption or intravascular injection of 0.25% bupivacaine or any other preparation of amide local anesthetics

|   |  |
|---|--|
| Protocol Title:                           | QUADRATUS LUMBORUM II BLOCK VS CONVENTIONAL THERAPY ALONE FOR LAPAROSCOPIC SLEEVE GASTRECTOMY  |
| Principal Investigator Name/Contact Info: | [name] MD
[contact]   |
| Primary Contact Name/Contact Info         | [name] MD
[contact]
[contact]
[name] MD
[contact]
[contact]
[name] MD
[name] MD
[name] DO
[name] MD |
| Date Revised:                             | 1/10/2018  |
| Study Number:                             | IF 2203362   |

can result in both central nervous system (CNS) and cardiac toxicity. Signs of CNS toxicity include restlessness, anxiety, dizziness, tinnitus, blurred vision, or tremors leading to convulsions. Such signs of CNS toxicity cannot be detected when the patient is under general anesthesia. Signs of cardiac toxicity include atrioventricular block, ventricular arrhythmias, and cardiac arrest. Patients will be monitored continuously during and after the procedure and will be given immediate treatment for local anesthetic toxicity if they exhibit the signs. Furthermore, the injection is performed in a relatively avascular anatomical space and both intravascular injection and systemic absorption are relatively unlikely.

Misplacement of the needle into the peritoneum and/or bowel is possible. Ultrasound guidance will be used and if the proper visualization of the needle is not possible, the procedure will be discontinued.

Bruising at the site of injection is possible.

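### Patient and assessor are declared blinded, but only QL 2 patients carry a needle mark on each side, and nothing in the protocol conceals it

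*Protocol*

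**What the plan says.** Section 5 b) Recruitment Methods sets the standard: "This project will be a prospective double blinded randomized control trial", and "The patient and anesthesiologist assessing the patient will be blinded". The same section gives the supporting measures. "Then anesthesiologist performing the QL 2 block will be different from the anesthesiologist assessing the patient after surgery", and the resident who knows the allocation takes no part in the study. Section 5 f) adds that the research personnel who evaluate patients are blinded. Section 5 b) also mentions blinding assessments by the study team, without content or timing.

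The procedures differ in where they touch the skin. For controls, "Conventional therapy consists of the injection of 30 mL of bupivacaine 0.25% directly into the incision sites by the surgeon at the end of the" operation. For the block, "The QL 2 group will receive 15 mL bupivacaine 0.25% on both sides for a total of 30 mL once the surgery is done but" before extubation. Section 5 f) says that "the probe will be placed at the anterior superior iliac spine at the level of the mid-axillary line" and is then moved further back, after which a "10 cm, 21-gauge block needle will be inserted from an anterior to posterior direction followed by injection of 15 mL of bupivacaine 0.25% on each" of the two sides. Section 6 adds: "Bruising at the site of injection is possible".

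**The concern.** Blinding of the patient needs more than separating the staff. It needs the two arms to look alike to the patient, and here they do not. After a QL 2 block there is a puncture on each side, away from the midline and possibly bruised. After infiltration there are only the surgical incisions, which every patient has. Section 5 b) says the study is explained to patients and offers them a copy of the protocol, so a patient can know what a lateral puncture means.

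The assessor is exposed as well. In section 5 f) the evaluator who records VAS in the PACU also maps the block by pinprick, which means looking at the area where the marks may be.

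At stake are the outcomes that rest on the patient's own report. These are VAS up to 48 hours and, through the VAS condition for prn hydromorphone, the primary endpoint itself.

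**Working it through.** **1. The arms side by side**

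| | QL 2 | Control | Source |
|---|---|---|---|
| Skin entry | One 21-gauge puncture per side | Existing incisions only | 5 b), 5 f) |
| Position | Probe starts at the mid-axillary line, then moves postero-laterally | Port sites | 5 f) |
| Possible later trace | Puncture, bruise | None beyond the surgical wounds | 6 |
| Concealment described | None | None | 5 b), 5 f) |
| Patient's state at the time | Anesthetized | End of procedure | 5 b), 5 f) |

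Each stated safeguard can be checked against each person to be blinded. A separate block performer and an uninvolved resident stop allocation from passing through staff. Neither hides a mark from the patient, and neither hides it from an assessor who exposes the trunk.

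**2. From mark to outcome**

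VAS is a secondary outcome on PACU arrival and at 1, 2, 24 and 48 hours (5 e). Hydromorphone is given prn only for a VAS above 6 (5 f), so on whole-number scores a report of 7 meets the condition and a report of 6 does not. The primary endpoint totals postoperative opioid over 48 hours (5 e). A change in reporting can therefore reach both outcomes.

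**3. How many patients carry the sign**

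The allocation ratio is not stated, so 1:1 is assumed. The plan's own figure is reproduced first, with d = 0.7, two-sided alpha 0.05 and power 0.95:

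- Normal approximation: n per arm = 2(1.960 + 1.645)² / 0.7² = 2 × 12.995 / 0.49 = 53.04, rounded up to 54, or 108 in total.
- Two-sample t-test (noncentral t): 54.02, rounded up to 55, or 110 in total. This matches section 5 c) exactly.

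So 110 / 2 = 55 patients at most carry the marks in one arm, and none in the other. This counts patients with a puncture, not patients who are unblinded.

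**4. Sensitivity of the test to a reporting shift (illustration only)**

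The documents give no shift, so the values below are assumed. Suppose there is no true effect and a difference of b SD in opioid use arises from reporting alone. With 55 per arm, the noncentrality is b × √(55/2) = 5.244 b, and the chance of p < 0.05 is P(|t| > 1.982) on 108 degrees of freedom. The result is the same for either direction of shift.

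| b (SD) | 0.1 | 0.2 | 0.3 | 0.4 | 0.5 |
|---|---|---|---|---|---|
| Noncentrality | 0.52 | 1.05 | 1.57 | 2.10 | 2.62 |
| Chance of p < 0.05 | 8% | 18% | 34% | 55% | 74% |

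The nominal rate is 5%. Here b is the average over the whole arm. If half the QL 2 patients inferred their arm and each shifted by 0.4 SD, b would be 0.5 × 0.4 = 0.2. The table shows that shifts well below the planned 0.7 would matter. It does not show that any shift occurs.

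**The case against.** Several counter-arguments are sound and limit the point.

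- **The block is done under anesthesia.** The patient does not witness it. Unblinding can come only from marks or soreness found later, and whether patients with fresh surgical wounds would notice or correctly interpret them is unknown.
- **The exact site is an inference.** The protocol never says flank, and the needle enters from the front of the probe. The text supports a lateral puncture on each side. It does not fix the distance from the ports.
- **The skin-prep cue is weak.** Chlorhexidine preparation is specified for the QL 2 group only, but it is applied to an abdomen that has just been operated on, and nothing says it leaves a visible trace.
- **Blinding measures exist.** Staff are separated, and blinding assessments are mentioned. But separation does not hide marks, and an assessment measures unblinding without preventing it.
- **This is missing detail, not a contradiction.** No sentence denies the blinding. But hiding a procedure is a matter of trial conduct that the protocol fixes, and no later analysis can restore it.

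A reader might also infer that the bias favors QL 2 and that a report of 6 in place of 7 removes a rescue dose. The documents support neither. The comparator is active, with the same drug, concentration and total volume, and section 8 says the benefits of QL 2 in bariatric surgery are unknown and there may be none. Hydromorphone is prn, so a lower report at one moment may only delay a dose.

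**Conclusion.** The point stands in a limited form. Followed as written, the protocol leaves a sign of allocation on up to 55 of 110 patients (1:1 assumed) and describes nothing to conceal it from the patient or the pinprick examiner. The outcomes it could affect rest on self-report. That patients or assessors can read the arm outright is a stronger claim than the text allows: unblinding is possible, not certain. The number unblinded and the size and direction of any bias cannot be derived from the documents, and the percentages above rest on assumed shifts. The change is worth making because it is cheap and, once patients have been treated without it, the loss cannot be recovered.

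**What to change.** In sections 5 b) and 5 f), state that before emergence every patient in both arms receives identical small opaque dressings at the QL 2 puncture positions on both sides. The dressings stay on until the 48-hour VAS, and the sensory exam is done around them.

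Give the blinding assessments in section 5 b) a definition. Ask the patient and the assessor which treatment they think was given, once early (for example at the end of the PACU evaluation) and again at 48 hours, and report the answers by arm. The early question matters because a guess taken only at 48 hours is mixed with the pain relief already experienced.

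The cost is two dressings and a few minutes per patient, the guess questions, and a slightly smaller area for pinprick. No sham needle is needed, and no drug, dose or rescue rule changes. Masking stays incomplete: dressings do not hide a large bruise, soreness or the pattern of numbness. If the guesses show unblinding, the double-blind description should be qualified in the report.
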